7.8. Risk Mitigation

There are no specific risks that are being mitigated by any specific action.

8. CORRELATIVE / SPECIAL STUDIES

8.1.1. Assessment of desmoid tumor response using the Nanostring CosMX SMI

It is intended that subject specimens will be used in correlative studies. If subjects elect to opt-in to optional sample collection, then an archival tumor specimen will be requested at screening, and biopsies will be obtained at the time of cryoablation for correlative studies.

We propose to study the response of desmoid fibromatosis lesions to nirogacestat as part of the Sarcoma00061 trial at Stanford. Pre-existing diagnostic FFPE samples from the same patients will be compared to biopsies post-nirogacestat treated desmoid tumors using the Nanostring CosMX SMI. The post-Nirogacestat samples will be obtained with informed consent at the time of the cryoablation procedure that is part of the trial. This Nanostring tool allows for gene expression levels for 1,000 genes in individual cells on FFPE tissue sections with simultaneous expression of 64 proteins on an adjacent section. The analyzed 1,000 genes are involved in many processes in tumor biology but can also be used to extrapolate to genome-wide expression levels using a tool developed by the group of [name] at Stanford (Vahid et al. *Nature Biotechnology*, 2023). With this in-depth analysis we will be able to study the pathways targeted by treatment with Nirogacestat but also changes in the varying allele fraction (VAF) and changes occurring in the tumor microenvironment upon treatment. The findings will be validated by orthogonal technologies such as immunohistochemistry to quantify cells with nuclear beta-catenin expression (for VAF) and through correlation with in-vitro studies on desmoid tumors in the [name] laboratory.

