1.2. Background

1.2.1. Study Disease

Desmoid tumor is a non-metastasizing but locally aggressive neoplasm that can occur anywhere throughout the body. Desmoids are rare with an estimated incidence in the general population of 2 to 4 per million population per year.² Affected populations can occur in any age group, most commonly seen between the ages of 15 to 60, with a slight preponderance among women than men. Affected locations can include upper and lower extremities, trunk, head and neck region, abdominal wall, and intra-abdominal. The natural history of desmoid is extremely

variable and there are some tumors that spontaneously regress, some that remain stable for years, and some that have unrelenting growth. Tumors that occur intra-abdominally and are associated with familial adenomatous polyposis (FAP) tend to be multi-focal, more aggressive, and potentially fatal. Under histologic exam, desmoid tumors appear as spindle cells in an abundant fibrous stroma with low cellularity, few mitotic figures, and absent necrosis. Staining for nuclear beta-catenin is commonly seen and a fair amount of desmoids have mutations in Catenin Beta 1 (CTNNB1). Other mutations seen are adenomatous polyposis coli (APC) mutations, which are found in FAP patients.

For growing desmoid tumors, options include surgical resection (which can be morbid and has a high recurrence rate), radiation therapy, systemic therapy [such as chemotherapy or vascular endothelial growth factor receptor tyrosine kinase inhibitors (VEGF-TKIs)], and more recently, ablation procedures, such as cryoablation or high intensity focused ultrasound (HIFU).

However, each approach has its pros and cons. For radiation therapy, local control rates are excellent, with approximately 80% at 3 years, however, there are potentially devastating albeit rare long-term side effects such as secondary malignancies.³ For systemic therapy, the time to response is longer (sorafenib trial median of 9 months), and there is associated systemic toxicity. Chemotherapy (doxil, methotrexate/vinblastine) have higher response rates and faster time to response; however, they have more significant side effects than TKIs. For ablation procedures, it may not be technically feasible to totally treat the tumor due to proximity to critical structures such as nerve and skin, there is often a need for multiple treatment sessions. Tumor recurrence or progression is inevitable for tumors that cannot be completely ablated.

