1.2.3. Nirogacestat Overview, Indications, and Mechanism of Action

This information is from the nirogacestat Investigator's Brochure.⁴ Please also reference the OgsiveoTM (nirogacestat) package insert.²⁸

Nirogacestat (PF-03084014) is a potent, small molecule, selective, reversible, non-competitive inhibitor of γ -secretase (GS). Nirogacestat is being investigated for the treatment of desmoid

tumors. The rationale for developing a GS inhibitor in the desmoid tumor indication is supported by evidence that Notch signaling, activated by GS cleavage, is a growth driver in desmoid tumors and contributes to growth and proliferation of a wide range of cell types. An additional potential mechanism of action involving GS inhibition by nirogacestat is the prevention of the release of cytoplasmic β catenin by blocking the proteolytic cleavage of cadherin complexes (Marambaud et al. 2002; Jang et al. 2011). This well conserved feature of cell-cell adhesion is an important factor in the regulation of Wnt signaling. The critical components of this regulation of the Wnt pathway are active in DT. Collectively, these observations support a therapeutically relevant mechanism of nirogacestat mediated GS inhibition that reduces activated Notch and possibly β -catenin signaling resulting in antiproliferative and apoptotic responses.

There is obligatory signaling via the Notch receptor in normal cells, which serves as a key regulator of cell differentiation, proliferation, and apoptosis. Aberrant signaling via the Notch pathway is known to be tumorigenic.

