8.1.3. Handling of Specimens

- Archival tumor sample will be ordered by [name] Research Coordinator (CRC). After deidentification (to the minimum information necessary) of the archival tumor sample by the CRC, the sample will be taken to [name] [name]'s laboratory for analysis.
- Biopsies:
 - Prior to collection: Record the required information (subject identification) on the biopsy specimen containers.
 - Biopsies obtained at the time of cryoablation will be placed in small containers with 10% buffered formalin. Biopsy specimen(s) will then be transferred from the MR

procedure room to [name] [name]'s laboratory, where the specimen(s) will be embedded in paraffin blocks and sections will be cut for H&E staining, immunohistochemistry, and Nanostring SMI analysis. Biopsies will be kept at room temperature for transport to [name]'s laboratory.

- [name] clinical research coordinator (CRC) will pick up the samples from the MR procedure room and transport them to [name]'s laboratory.
- A requisition form will be used to document the transfer of the biopsy specimen(s) from the MR procedure room to [name] [name]'s laboratory. The following will be included in the requisition form:
 - Subject study identification number, and other required information per Pathology Laboratory.
 - Name and signature of person picking up biopsy specimen(s) from MR procedure room for transfer to [name]'s laboratory, and date and time of biopsy specimen(s) pick-up.
 - Name and signature of person receiving biopsy specimen(s) at [name]'s laboratory, and date and time biopsy specimen(s) was/were received.

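### Section 8.1.1 promises changes in allele fraction (VAF), but the assays it names are described as reading expression and protein location, and the staining marker offered for VAF may itself respond to nirogacestat

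*Protocol*

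**What the plan says.** Protocol section 8.1.1 sets up a paired comparison: "Pre-existing diagnostic FFPE samples from the same patients will be compared to biopsies post-nirogacestat treated desmoid tumors". The main platform is described in these terms: "This Nanostring tool allows for gene expression levels for 1,000 genes in individual cells on FFPE tissue sections", together with 64 proteins on an adjacent section. From this analysis the section expects to study the pathways that the drug targets, "but also changes in the varying allele fraction (VAF) and changes occurring in the tumor microenvironment upon treatment". Validation is to come from methods such as "immunohistochemistry to quantify cells with nuclear beta-catenin expression (for VAF"), and from correlation with in-vitro work.

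Section 8.1.3 gives the handling of the biopsy: "sections will be cut for H&E staining, immunohistochemistry, and Nanostring SMI analysis". No DNA-based or other allele-specific assay is named there or in the schedule of events.

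Section 1.2.3 describes a further potential mechanism of nirogacestat, in which cytoplasmic beta-catenin is not released, "by blocking the proteolytic cleavage of cadherin complexes". It concludes that gamma-secretase inhibition "reduces activated Notch and possibly β -catenin signaling resulting in antiproliferative and apoptotic responses".

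Section 1.2.1 lists staining and mutation as separate findings: "Staining for nuclear beta-catenin is commonly seen and a fair amount of desmoids have mutations in Catenin Beta 1", with APC mutations found in patients with familial adenomatous polyposis.

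**The concern.** An allele fraction is a property of DNA. A count of cells with nuclear beta-catenin is a fraction of cells, defined by where a protein sits. The second can stand in for the first only if the link between carrying the mutation and staining positive is the same in both samples being compared.

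Here the two samples differ by design in drug exposure: one predates nirogacestat and the other follows three cycles of it. The protocol itself says the drug may act on beta-catenin. So the marker chosen to support the VAF result lies on a pathway that the treatment may change.

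At stake is the interpretation of the correlative study. Suppressed signaling in surviving mutant cells and a smaller share of mutant cells are different findings. The exploratory objective is to correlate changes during treatment with response, so a wrong label could carry through to the reported conclusion.

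**Working it through.** The protocol states no figure for VAF, staining or their change, so there is nothing to reproduce. The check compares sections and then illustrates the size with assumed values.

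**Sections side by side**

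1. Claimed output: change in VAF after treatment (8.1.1).
2. Measured quantities: RNA for 1,000 genes, 64 proteins, nuclear beta-catenin by immunohistochemistry, and H&E (8.1.1, 8.1.3). None is described as an allele measurement, and the protocol does not explain how VAF would be obtained from them.
3. Validation named for VAF: the nuclear beta-catenin cell count (8.1.1).
4. Drug action: possible reduction of beta-catenin signaling (1.2.3).
5. Timing: archival sample before the drug; biopsy at cryoablation, between Cycles 3 and 4.

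Items 3 to 5 together mean that the named check may share the bias it would need to detect.

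**Why the staining count does not identify the change in VAF**

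Let m be the fraction of cells carrying a heterozygous diploid mutation and s the fraction of those cells that stain. Assume for simplicity that only mutant cells stain. Then:

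- true VAF = m / 2
- stained fraction F = m × s
- stain-implied VAF = F / 2 = m × s / 2

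The ratio of F after treatment to F before is (m₁/m₀) × (s₁/s₀). It equals the change in mutant fraction only if s₁ = s₀. The factor of 2 cancels in this ratio, so the problem is not that a cell fraction differs in scale from an allele fraction. The problem is that s may move with the drug.

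**Illustration (all values assumed; none is in the protocol)**

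- m = 0.80 before and after, so true VAF = 0.80 / 2 = 0.40 at both times.
- Before: s = 0.95, so stain-implied VAF = 0.80 × 0.95 / 2 = 0.38.
- After, if s falls to 0.80: 0.80 × 0.80 / 2 = 0.32, an apparent fall of 0.06.
- After, if s falls to 0.50: 0.80 × 0.50 / 2 = 0.20, an apparent fall of 0.18.
- After, if s stays at 0.95: 0.38, an apparent change of 0.

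The apparent fall in VAF therefore runs from 0 to 0.18 over this range, with no change in alleles in any case.

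**The case against.** The strongest reply is that little depends on this. VAF appears only in 8.1.1. It is in no objective or endpoint, the exploratory analysis in 10.2.3 covers EQ-5D-3L only, and tissue collection is opt-in. That stands, and it keeps the point small.

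A second reply is that the wording is open and hedged. The validation methods are introduced as examples, in-vitro correlation is a further route, samples may be saved for future research, and the effect on beta-catenin is only a possible one. Section 8.1.1 also lists targeted pathways as a separate aim, so a pharmacodynamic reading is already in scope. All this stands. It limits the conclusion to what could happen, but staining remains the only method named for VAF.

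A third reply is that the surrogate has some rationale: section 1.2.4 reports APC or CTNNB1 mutations in 15 of 17 subjects (88%) in the earlier phase 2 study. That supports a link between staining and mutation in general. It does not show that the link is unchanged after three cycles of the drug.

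A reader might infer more than the documents support:

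- That an allele fraction can never be derived from CosMX. The protocol describes the platform briefly and cites an extrapolation tool; what else either can do cannot be judged from it.
- That a drug effect would be reported as clonal change. The mechanism is hedged, and no rule for reporting VAF is given.
- That pathway suppression and tumor cell loss are opposite conclusions. Section 1.2.3 links reduced signaling to antiproliferative and apoptotic responses, so they may be steps in one process. They are different, not opposite.

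**Conclusion.** The point holds in a limited form. Section 8.1.1 states that the correlative analysis will show changes in VAF and be validated for VAF by nuclear beta-catenin staining. The named assays, as the protocol describes them, do not support that claim. On the protocol's own account of the drug, a fall in nuclear staining could occur in unchanged mutant cells and be mistaken for a fall in VAF. This is a claim made in the protocol, not a detail left for a later analysis plan.

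The size is unknown. The apparent fall of 0.06 to 0.18 rests on assumed values for mutant fraction and staining, and the error is zero if the drug leaves staining unchanged. The number of pairs affected is also unknown, because tissue is opt-in among up to 23 enrolled subjects. No primary or secondary endpoint, sample size or decision rule is touched. It is a minor but worthwhile correction.

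**What to change.** In section 8.1.1, remove VAF as an output of CosMX and immunohistochemistry. Name the staining measure as the fraction of cells with nuclear beta-catenin, classify it as a pharmacodynamic readout, and state that a change in it will not be interpreted as a change in mutant-cell or allele fraction.

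This is a wording change that needs no new sample, visit or procedure. Its cost is giving up a VAF claim that the named assays do not support. If VAF is still wanted, the section should name a DNA-based assay on the paired samples, for example CTNNB1/APC sequencing of the same paraffin blocks. That would depend on leftover tissue and on consent for DNA work, neither of which can be checked from the document.

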8.1.2. Collection of Specimens

If subjects elect to opt-in to optional blood and tissue collection for correlative studies:

- Archival tumor sample will be requested from pathology and may be saved for future research.
- Biopsies will be obtained at the time of cryoablation (between Cycle 3 and 4) for correlative studies. Biopsies may be saved for future research.

8.1.3. Handling of Specimens

- Archival tumor sample will be ordered by [name] Research Coordinator (CRC). After deidentification (to the minimum information necessary) of the archival tumor sample by the CRC, the sample will be taken to [name] [name]'s laboratory for analysis.
- Biopsies:
 - Prior to collection: Record the required information (subject identification) on the biopsy specimen containers.
 - Biopsies obtained at the time of cryoablation will be placed in small containers with 10% buffered formalin. Biopsy specimen(s) will then be transferred from the MR

procedure room to [name] [name]'s laboratory, where the specimen(s) will be embedded in paraffin blocks and sections will be cut for H&E staining, immunohistochemistry, and Nanostring SMI analysis. Biopsies will be kept at room temperature for transport to [name]'s laboratory.

- [name] clinical research coordinator (CRC) will pick up the samples from the MR procedure room and transport them to [name]'s laboratory.
- A requisition form will be used to document the transfer of the biopsy specimen(s) from the MR procedure room to [name] [name]'s laboratory. The following will be included in the requisition form:
 - Subject study identification number, and other required information per Pathology Laboratory.
 - Name and signature of person picking up biopsy specimen(s) from MR procedure room for transfer to [name]'s laboratory, and date and time of biopsy specimen(s) pick-up.
 - Name and signature of person receiving biopsy specimen(s) at [name]'s laboratory, and date and time biopsy specimen(s) was/were received.

8.1.4. Coding of Specimens for Privacy Protection

At the time of enrollment, each subject will be given a specific confidential study identification number. Specimens will be stored under subject study identification number. The information can be shared with other investigators listed on this protocol. Study data will be maintained in password protected computer files (protected online database). Only research personnel will have access to this information.

9. REGULATORY CONSIDERATIONS AND DATA REPORTING

Treatment may continue via this study protocol for up to 24 months (26 cycles of treatment), unless there is progression of disease, intolerance, start of new anticancer therapy (as defined in Section 5.7.2), or one of the criteria in Section 3.7 (Subject Study Completion or Termination) occurs. After 24 months of treatment, if clinically indicated, a subject may transition to commercial nirogacestat supply, once the subject has completed the End of Treatment (EOT) visit and is off study.

9.1. Review and Approval of Protocol by IRB and SCI SRC

This protocol, the proposed informed consent, and all forms of information related to the study that will be provided to the subjects (eg, questionnaires, handouts, written instructions, diaries, advertisements used to recruit subjects, etc.) will be submitted to, reviewed, and approved by the SCI Scientific Review Committee (SRC) and the Stanford Administrative Panels on Human Subjects in Medical Research of the Research Compliance Office (ie, the Stanford IRB) prior to initiation of the research. Any changes made to the protocol will be submitted as a modification and will be approved by the IRB of record prior to implementation.

This study will be conducted in accordance with the iteration of the protocol that is currently IRB-approved.

9.2. Protocol Compliance and Deviations

9.2.1. Compliance with the Protocol

No deviation or changes from the procedures and process described by the IRB-approved protocol, except those necessary to eliminate an immediate hazard(s) to trial subjects, or when the change(s) involves only logistical or administrative aspects of the trial [eg, change in study monitor(s), change of telephone number(s)], will be knowingly permitted without review and approval by the IRB of record.

9.2.2. Protocol Deviations

Any deviation (or violation) from the IRB-approved protocol, including those that eliminate an immediate hazard or are administrative in nature, will be documented and explained in the study site file. All deviations at the Stanford clinical site that meet the reporting requirements defined in the Stanford University HRPP Policy Guidance “Events and Information that Require Prompt Reporting to the IRB” GUI-P13 will be reported to the Stanford IRB by the Stanford investigator within the defined timeframes. All deviations will be reported to the Stanford IRB either annually in the IRB continuing review, or individual as IRB Prompt Reports (within 5 or 10 working days, see GUI-P13).

For all studies monitored by the SCI Data and Safety Monitoring Committee (DSMC) as defined in Section 9.3 Data and Safety Monitoring Plan, all deviations, exceptions, and/or violations of the protocol, as well as deviations, exceptions, and/or violations to applicable IRB policies and overarching regulations, will be reported to the SCI Data Safety and Monitoring Committee (DSMC). Accordingly, as the DSMC only reviews reports recorded in OnCore, such events will be promptly submitted in the OnCore record for the study, per the current SCI DSMC SOP.

The principal investigator (PI) will review deviations on a weekly basis with the Clinical Research Coordinator, including a description of the deviation(s), the date the PI became aware of the deviation, the date the deviation was reported to Oncore and whether or not the deviation required prompt reporting to the IRB, the determination of the deviation root cause, and determination if a corrective action plan (CAP) is needed. Weekly review will include discussion of any recurring deviations. Aggregate data will be used to evaluate trends.

9.3. Data and Safety Monitoring Plan

The Principal Investigator is responsible for monitoring the conduct of the study including oversight of safety and protocol compliance. On an ongoing basis, the Principal Investigator will review safety data and identify any changes to the research necessary to ensure the appropriate measures and monitoring necessary for participant safety. In addition to the Principal Investigator's safety monitoring role, the SCI DSMC will conduct data and safety monitoring activities for this study.

9.3.1. Monitoring

In addition to investigator self-monitoring (Section 9.3.1.1), the SCI DSMC will monitor study-related activities to determine whether the study has been conducted in accordance with the protocol, local standard operating procedures, FDA regulations, [GCP, and SOPs](#). In addition, the DSMC will regularly review serious adverse events and protocol deviations associated with the research to ensure the protection of human subjects. Results of DSMC monitoring activities will be communicated to the investigator, who has the responsibility to provide such reports to the IRB of record and the appropriate regulatory authorities at the time of continuing review, or in an expedited fashion, as needed.

9.3.1.1. **Investigator Monitoring**

Pursuant to the Guideline for [GCP](#), monitoring is defined as the act of overseeing the progress of a clinical trial, and of ensuring that it is conducted, recorded, and reported in accordance with the protocol, standard operating procedures (SOPs), GCP, and the applicable regulatory requirement(s).

The Principal Investigator is responsible for self-monitoring the progress of the trial on a continuous basis. Monitoring may be delegated to an appropriately trained individual (local monitor). The local monitor will prepare a report and provide it to the Principal Investigator/IND holder. This report will be filed with study documentation. The PI/IND holder will review the monitoring findings and determine any needed actions. Self-monitoring includes, but is not limited to, those items that will be reviewed during an audit (see also Section 9.5). Critical data will be monitored from 1 out of every 6 study participants, including but not limited to consent, eligibility, safety, and study participant on-treatment and off-treatment dates. Efficacy endpoints will be assessed at the end of the trial once all patients have been on study long enough to reach the primary endpoint. The monitoring will be adequate to assure that the valid consent is obtained and documented; the per-protocol data is collected; records and databases are maintained with adequate and accurate participant case histories; adverse events are reported; clinical protocol is maintained; and the study is conducted according to the established procedures of the IRB.

9.4. **Data Management**

Source documents for all research data will be retained in accordance with all applicable regulations and institutional requirements for data retention. These materials will be made available for monitoring and/or auditing by SCI DSMC, other monitoring body and/or regulatory agencies.

9.4.1. **Data Management Plan**

A chart with all of the relevant research subject information will be maintained for each subject by the CRC. Subject paper source records will be kept in a secure location at Stanford University Medical Center. The study data will be transcribed and retained in the Oncore central online database, with password protected access limited to the study team of each clinical site. Clinical site is expected to have and maintain the original source document or record for verification of all research data. Data will be temporarily locked for the primary outcome

assessment after the last subject has completed the timeframe for primary outcome. Final database lock will be once all subjects have completed all study visits.

Source documents include but are not limited to:

- Consent document
- Regulatory documents
- Medical history
- Archival tumor sample pathology report
- Physician notes
- Treatment records
- Laboratory reports
- Any other ancillary reports as required by protocol
- Pharmacy records
- Radiology reports
- Tumor measurements
- Vital signs
- Concomitant medications
- Adverse event assessments
- All other protocol-specified tests and data event assessments
- Questionnaire

The Protocol Director must maintain adequate and accurate participant case histories with observations and other data pertinent to the study. The Protocol Director will be responsible for maintaining the clinical protocol and subjects' study charts, reporting adverse events, assuring that consent is obtained and documented, and reporting the status of the trial in continuing renewals submitted to the IRB.

